Study Title: Whey Protein Support to Metabolic and Performance Adaptations in Response to High Intensity Interval Training in Young Adult Men

NCT: 7867835

Date: 14th May 2018

Detailed study protocol 7867835

Baseline screening

Prior to experimental testing, participants will attend the lab to complete baseline screening including an incremental cycle ergometer test to exhaustion to determine maximal oxygen update (VO₂max) via indirect calorimetry. A body composition assessment via bioelectrical impedance analysis (BIA) will also characterise participants for inclusion in the study (BMI <30 kg.m⁻²). The protocol to determine VO₂max comprises a 5 minute warm-up stage at 50 W with subsequent 1 minute incremental stages (30 W) until exhaustion. The following criteria are used to establish if VO₂max has been achieved: Volitional fatigue, Rate of perceived exertion (RPE) \geq 18, respiratory exchange ratio (RER) \geq 1.10, and heart rate (HR) \geq 85% age-predicted max.

Pre-intervention performance testing

Following baseline screening, included participants attend the lab 2 h after a standardised meal and having refrained from caffeine on the day of testing, to complete pre-intervention performance testing. This comprises in order a baseline i) Wingate test; ii) Submaximal incremental cycling test; iii) 20 minute cycling performance test.

Wingate Test

After recording height and weight, participants complete a standardised 5 minute warm-up on a Wingate cycle ergometer, followed by 30 s maximal cycle sprinting against a resistance equivalent to 7.5% of their body mass (BM). A 3 minute cool down period follows this test.

Submaximal incremental cycling test

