This study will be conducted in a randomised, double-blind (participants and outcomes assessor blind) parallel groups design. Participants are randomly allocated into one of 3 nutritional intervention groups; fasted placebo, WPC fed or WPH fed. The exercise intervention comprises 9 HIIT sessions completed over 3 weeks with 48h rest in between exercise sessions. HIIT sessions will consist of 4-6 (4 sprints in the initial 3 sessions, 5 sprints in the middle 3 sessions, and 6 sprints in the final 3 sessions) X 30s maximal cycle sprints on a Wingate cycle ergometer, pedalling at a resistance equivalent to 7.5% BM. Each sprint is interspersed with 4 minutes active recovery. Standardised 5 minute warm-up and 3 minute cool-down periods precede and follow each exercise session, respectively. On the morning of each exercise session, participants arrive to the lab after a $\geq 10h$ overnight fast, having abstained from caffeine for 12h, alcohol intake for 24h and vigorous exercise 48h beforehand. On the morning of exercise session 1, a resting micro-needle muscle biopsy will be obtained under local anaesthetic (1% lidocaine) from m. vastus lateralis, as well as a venous blood sample. Following this, participants ingest the allocated pre-exercise drink and rest quietly in the lab for 45 minutes before beginning exercise. Further venous blood samples are obtained immediately pre and post-exercise. For exercise session 1, HIIT comprises 4 X 30s "all out" Wingate sprints, interspersed with 4 minutes active recovery. A fourth venous blood sample is obtained 1 h postexercise, as well as a second muscle biopsy, which is obtained 3 h post-exercise using the same procedures as before. Between the post-exercise recovery period and second muscle biopsy, participants are not permitted any food or drinks except for consuming water ad libitum. For the remaining exercise sessions, participants arrive the lab under the same conditions, ingest their allocated pre-exercise drink and rest quietly for 45 minutes before completing HIIT. They are also

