provided with a standardised snack (2.43kcal.kg⁻¹ BM, 0.25g.kg⁻¹ BM protein) to consume 30 minutes following post-HIIT. Following HIIT session 9, a final muscle biopsy and venous blood sample are obtained 48-72h post-exercise under the same conditions (overnight fasted) and using the same procedures. Anaerobic exercise performance markers are obtained for each HIIT session (exercise sessions 1-9) as well as for individual sprints within-session (sprints 1-6) including peak power, mean power, total work and fatigue index.

Post-intervention performance testing

The performance testing completed pre-intervention (pre-intervention performance testing) is repeated by participants in an identical manner 72-96 h following completion of the final HIIT session. 24 h dietary recall is repeated for this lab visit, and participants refrain from caffeine intake and attend the lab 2 h following a standardised meal.

Statistical Analysis Plan

Normality and homogeneity of variance are tested prior to statistical tests. Paired sample t-tests will be used to assess within group changes. Between group treatment effects will be evaluated using a One-way ANOVA to examine the main effects of treatment based on delta scores from pre to post intervention. If the ANOVA yields a significant effect, post hoc comparisons will be performed using a bonferroni correction. A probability level P < 0.05 will be considered statistically significant and *cohen's d* effect sizes will be calculated. All normal data will be expressed as Mean ± Standard Deviation/Standard Error, or non-parametric as median (Interquartile Range).

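### The between-group ANOVA on change scores is valid, but a prespecified baseline-adjusted ANCOVA could gain precision at little cost if the pre-post correlation is moderate and the SDs are similar

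*Combined protocol and SAP*

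**What the plan says.** The Statistical Analysis Plan section of the combined protocol and SAP is one paragraph. Within arms, "Paired sample t-tests will be used to assess within group changes". Between arms, treatment effects are to be "evaluated using a One-way ANOVA to examine the main effects of treatment based on delta scores from pre to post intervention". Then: "If the ANOVA yields a significant effect, post hoc comparisons will be performed using a bonferroni correction". The threshold is given as "A probability level P < 0.05 will be considered statistically significant". No baseline covariate or other baseline-adjusted model is mentioned anywhere.

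The baseline values are already collected:

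- **Performance tests.** Participants attend "to complete pre-intervention performance testing" (Wingate, submaximal incremental and 20 minute tests) before the HIIT programme. Under Post-intervention performance testing, "The performance testing completed pre-intervention (pre-intervention performance testing) is repeated by participants in an identical manner".
- **Biopsy and blood.** Under Experimental design, the resting biopsy and first venous sample of session 1 come before the first allocated drink: "Following this, participants ingest the allocated pre-exercise drink and rest quietly in the lab for 45 minutes before beginning exercise". Both are repeated, fasted, 48-72 h after session 9.
- **HIIT session and sprint markers.** These are recorded in sessions 1 to 9. Because session 1 is performed after the allocated drink, they have no untreated baseline.

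**The concern.** A change score uses the baseline by subtraction, which is the same as assuming that post rises one-for-one with pre. The actual slope is rho x SD_post/SD_pre. When this is below 1, subtraction over-corrects, with two consequences. The comparison of whey protein concentrate, whey protein hydrolysate and placebo has wider intervals than the same data could give. And if the arms differ at baseline by a chance amount D, the estimated contrast moves by (slope - 1) x D in that particular trial, although it averages to zero over randomisations.

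What is at stake is precision in a three-arm trial. The validity of the planned test is not in question.

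**Working it through.** **Inputs.** From the documents: three randomised parallel arms, change-score ANOVA, threshold 0.05. Arm size, rho, SDs and effect size are not given, so there is no planned figure to reproduce. Everything below is an assumption shown over a range: n per arm, equal arms, normal data, and a common linear slope.

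**Variance ratio.** Let k = SD_post/SD_pre. For a contrast between two arms,

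Var(ANCOVA)/Var(change) = [k²(1 - rho²) / (1 + k² - 2·rho·k)] x [1 + 1/(3n - 5)].

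The second factor is the cost of estimating the slope. Since k²(1 - rho²) = (1 + k² - 2·rho·k) - (1 - rho·k)², the first factor never exceeds 1, and it equals 1 only when the slope rho·k is exactly 1. With k = 1 it reduces to (1 + rho)/2.

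Example, n = 10, rho = 0.5, k = 1: 0.75 x (1 + 1/25) = 0.75 x 1.04 = 0.78.

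| n per arm (k = 1) | rho 0.5 | rho 0.7 | rho 0.9 | rho 0.95 |
|---|---|---|---|---|
| 8 | 0.79 | 0.89 | 1.00 | 1.03 |
| 10 | 0.78 | 0.88 | 0.99 | 1.01 |
| 15 | 0.77 | 0.87 | 0.97 | 1.00 |

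**Interval width.** ANCOVA also spends one error degree of freedom (at n = 10, 26 instead of 27). Including that, the 95% CI width ratio at n = 10 is 0.885, 0.942, 0.996 and 1.009 for the four correlations. Widths break even at rho of about 0.89, 0.92 and 0.95 for 8, 10 and 15 per arm.

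**Unequal SDs, n = 10.**

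- k = 1.2, rho 0.5: 1.44 x 0.75 / (2.44 - 1.20) x 1.04 = 0.91.
- k = 1.2, rho 0.7: 1.44 x 0.51 / (2.44 - 1.68) x 1.04 = 1.005, so no gain.
- k = 0.8, rho 0.7: 0.64 x 0.51 / (1.64 - 1.12) x 1.04 = 0.65.

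**Omnibus F-test, simulated, n = 10, k = 1, both whey arms shifted by one change-score SD.** That shift is sqrt(2(1 - rho)) raw SD, so 1.00, 0.77, 0.45 and 0.32 raw SD at rho 0.5, 0.7, 0.9 and 0.95. Power of the change-score ANOVA is 0.58 throughout. Power of ANCOVA is 0.69, 0.64, 0.59 and 0.58. With a shift of only 0.3 raw SD, power is 0.09 against 0.11 (rho 0.5) and 0.125 against 0.139 (rho 0.7). Simulated type I error for 8 to 20 per arm and rho 0.3 to 0.95 was 4.9% to 5.1% for the change-score test and 4.8% to 5.2% for ANCOVA.

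**Chance imbalance.** The baseline difference between two arms of 10 has SD sqrt(2/10) = 0.447 raw SD. With k = 1, a difference of that size moves the change-score contrast by (rho - 1) x 0.447: -0.22 SD at rho 0.5, -0.13 at 0.7 and -0.04 at 0.9.

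**The case against.** The strongest reply is that there is no defect. The SAP prespecifies a standard test with correct error rates, and the conditional shift is ordinary sampling variation that those error rates already cover. Whether this trial would benefit is also unknown. The tests are repeated identically, under the same meal and caffeine controls, after three weeks, and outcomes such as absolute power and total work may correlate at 0.9 or more. A moderate rho is not sufficient either: at rho 0.7 and 10 per arm the gain in interval width is gone once the post SD exceeds the pre SD by about 18%. Quoting variance ratios flatters the gain, since the intervals narrow by only about 6% at rho 0.7 and 11% to 12% at rho 0.5. Finally, ANCOVA brings a linear, common-slope assumption, and the planned Cohen's d would need a new definition.

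All of this is factually right, and it is why the point is an optional improvement. It does not remove the case for the change, because the trade is lopsided. At 10 per arm the worst loss is 4% in variance (about 2% in interval width) whatever rho and the SD ratio are, against a saving of 12% to 22% in variance at rho 0.5 to 0.7 with equal SDs. One method is to serve many outcomes (power, lactate threshold, economy, biopsy and blood measures), which need not share one high correlation. Not knowing the slope is a reason to estimate it. The common-slope and effect-size points are details for the SAP wording.

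**Conclusion.** The point holds as an efficiency improvement, to be considered and not required. The planned change-score ANOVA is valid. ANCOVA on the pre-intervention value would give tighter between-group comparisons if rho is moderate (about 0.5 to 0.7) and the pre and post SDs are similar. It would make little or no difference if rho is about 0.9 or higher, or if the post SD is enough larger than the pre SD to bring the slope near 1. The size of the gain here cannot be settled from the documents, because it rests on assumed arm sizes, correlations and SDs. It applies only to outcomes measured before the first allocated drink, and it would not make the trial adequately powered for a small effect.

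**What to change.** For the repeated Wingate, submaximal and 20 minute tests, and for the resting biopsy and blood measures taken before and after the programme, replace the ANOVA on change scores with a prespecified ANCOVA: post-intervention value (or change) on treatment group, with the pre-intervention value of the same outcome as covariate. In the same text:

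- Keep the omnibus test and the Bonferroni contrasts, applied to adjusted means, and report adjusted differences with 95% CIs.
- Check normality and homogeneity of variance on the model residuals. Inspect post against pre by arm for non-linearity and high-leverage baselines.
- State which SD is the denominator of Cohen's d after adjustment.
- Do not use session 1 HIIT markers as a baseline covariate, because session 1 follows the allocated drink.
- Fix the choice before unblinding, so that the two analyses cannot be chosen between on their results.

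The cost is a few sentences in the SAP and no new data. Statistically it is one error degree of freedom and a variance inflation of 1/(3n - 5), which is 4% at 10 per arm. With equal SDs, intervals become marginally wider at that size only if rho exceeds about 0.92.

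### Is it an error to apply Bonferroni after a significant three-arm ANOVA, when a closed test could test each pair at 0.05?

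*Combined protocol and SAP*

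**What the plan says.** The Experimental design section fixes the number of arms: "Participants are randomly allocated into one of 3 nutritional intervention groups; fasted placebo, WPC fed or WPH fed". The Statistical Analysis Plan section then sets a two-step rule for each outcome. The first step is a global test: "Between group treatment effects will be evaluated using a One-way ANOVA to examine the main effects of treatment based on delta scores". The second applies only if the first succeeds: "If the ANOVA yields a significant effect, post hoc comparisons will be performed using a bonferroni correction". The threshold is stated once: "A probability level P < 0.05 will be considered statistically significant". Assumptions are checked beforehand: "Normality and homogeneity of variance are tested prior to statistical tests".

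The section does not say how many pairs are compared post hoc, which error term the comparisons use, or what follows if the homogeneity check fails. The document gives no sample size, SD, expected effect or power.

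**The concern.** The two steps appear to pay twice for the same protection. With three means, any two pairwise equalities imply the third. The only hypothesis that combines pairs is therefore equality of all three arms, and the ANOVA has already tested that at 0.05. By the closed-testing principle, each pair may then be tested at an unadjusted 0.05 with family-wise error still at 0.05. Dividing by three looks like power given away.

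What is at stake is the set of comparisons a reader wants: WPC against placebo, WPH against placebo, and WPC against WPH. All three are decided at the post hoc step. Bonferroni bears hardest on a claim that both whey products differ from placebo, because both pairs must then pass the stricter level.

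**Working it through.** **Inputs.** From the document: three arms, ANOVA on change scores, Bonferroni after a significant ANOVA, alpha 0.05. Assumed, because the document is silent: three pairs, two-sided tests, pooled ANOVA error, equal arms without dropout, normal data, equal SDs, and the effect sizes below. There is no design figure to reproduce.

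**Step 1: is the planned rule valid?** Per-pair level: 0.05/3 = 0.0167. Bound on family-wise error: 3 × 0.0167 = 0.05. If only the two whey-placebo pairs are meant, the level is 0.05/2 = 0.025 and the bound 2 × 0.025 = 0.05. Either reading controls error, so the unstated number of pairs does not threaten validity.

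Simulation (200,000 trials per scenario) agrees. Family-wise error is 0.041 to 0.043 when all arms are equal (8 to 30 per arm). It is 0.017 when one arm is far away; there the ANOVA is always significant and the single true null pair is tested at 0.0167. The closed test gives about 0.050 in both cases.

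**Step 2: what does the strictness cost?** Both whey arms +1 SD, pooled error, plan against closed test:

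| n per arm | Both whey effects | At least one whey effect |
|---|---|---|
| 8 | 16.5 v 31.0% | 42.9 v 47.1% |
| 10 | 24.1 v 41.0% | 53.8 v 58.0% |
| 15 | 44.5 v 63.3% | 75.1 v 78.5% |
| 20 | 62.9 v 79.1% | 87.8 v 90.0% |
| 30 | 86.7 v 94.4% | 97.6 v 98.2% |

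The gain is 8 to 19 points for both effects and 1 to 4 points for at least one. A single whey-placebo pair goes from 39% to 49% at 10 per arm and from 75% to 85% at 20.

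**Step 3: what does the alternative cost?** On a truly equal pair the error rises from 0.0167 to 0.05, a factor of 0.05/0.0167 = 3, for every outcome. The outcomes are many. The HIIT sessions alone yield several markers, "including peak power, mean power, total work and fatigue index", and there are also threshold, economy, time-trial, biopsy and blood measures. No primary outcome is named.

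The pooled closed test also leans harder on equal variances. Family-wise error, plan against closed test, SD ratio 1:1:2:

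- 10 per arm, all means equal: 0.054 v 0.064.
- 10 per arm, placebo = WPH and WPC far away: 0.034 v 0.082.
- Arms of 14/10/6 with the largest SD in the smallest arm: 0.114 v 0.124 (all equal) and 0.086 v 0.162 (WPC far away).

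**Step 4: does a Welch version remove that cost?** Only in part. Welch's ANOVA followed by Welch t-tests at 0.05 keeps error to about 5% with normal data. With skewed data and unequal SDs it reaches about 9% (arms 12/10/8, SDs 1/2/2), where the pooled plan has about 6%. It also returns some of the power: at 10 per arm, +1 SD, it gives 46.4% per pair, 37.4% for both and 55.3% for at least one, below the pooled closed test's 49%, 41% and 58%. With 6 per arm, at-least-one power is 30.5% under the plan and 30.4% under the Welch closure.

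**Step 5: do the gains survive other plausible readings?** With two post hoc pairs at 0.025 each and both whey arms at +1 SD, the plan against the Welch closure gives:

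- Per pair: 23.7 v 23.4% (6 per arm), 43.7 v 46.2% (10), 79.6 v 83.4% (20).
- At least one whey effect: 33.8 v 30.6%, 57.5 v 55.3%, 89.7 v 89.1%, a loss at each size.
- Both whey effects at 10 per arm: 30.2 v 37.3%, still a gain.

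With three pairs but effects of +0.5 SD, the per-pair gain from the Welch closure is 2.5, 4.0 and 5.6 points at 10, 15 and 20 per arm; at 10 per arm power goes only from 9.1% to 11.6%.

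**The case for a change.** The best case for changing the plan is that the logic is exact, the change takes two or three sentences before data are seen, and the gain in showing both whey effects is substantial: 41.0 − 24.1 = 16.9 points at 10 per arm with pooled error, or 37.4 − 24.3 = 13.1 points in the Welch form. The Welch form can also control error better than the plan. At arms of 12/10/8 with SDs 1/1/2 and all means equal, the pooled plan errs in 8.0% of trials and the Welch closure in 5.0%.

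The closure argument stands, and so do the figures for the scenarios assumed. They show that another valid procedure has more power for some claims; they do not show that the planned one gives a wrong answer. The 8.0% figure belongs to a different question, namely what the plan does if the homogeneity check fails. Bonferroni is not its cause: with Welch post hoc tests at 0.0167 after the same ANOVA, the error in that cell is 3.2%. Stating the number of pairs and the error term would make the SAP more precise, but that is missing detail, and the Bonferroni bound holds for two pairs or three.

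**Conclusion.** The concern does not hold. ANOVA followed by Bonferroni is a conventional rule and, when variances are similar, a valid one: family-wise error per outcome is about 4% when all arms are equal and about 1.7% when one differs greatly. It is conservative. In the illustrative case of 10 per arm and both whey arms at +1 SD, that costs about 17 points of power for showing both whey effects and about 4 for showing at least one. The closed test buys that power by tripling the error on a truly equal pair, across many outcomes with no named primary. It also becomes more sensitive to unequal variances or, in Welch form, to skew combined with unequal SDs. Reasonable statisticians could choose either.

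The power figures rest on assumed arm sizes and effects, since the documents give none, and mostly on three pairs, normal data and equal SDs. The closure argument applies to exactly three groups. Neither rule addresses multiplicity across outcomes, which is a separate matter.

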After 15 minutes seated rest, participants begin a submaximal incremental cycle test consisting of a 2 minute standardised warm-up followed by 4 minute stages starting at 50 W and incrementing by 50 W after each completed stage. The test ends after the final stage is completed, corresponding to a power output of 250 W, or when participants can no longer maintain a cadence of \geq 80 rpm during exercise. Participants must also maintain their cadence within a range of 80-85 rpm throughout the test. RPE and HR are used as markers of exercise intensity during this test. Capillary lactate is sampled at rest and during the final 30s of each stage and concentrations are determined using a handheld meter. Power output at the lactate threshold (W_{LT}) is calculated from this data. Cycling economy (CE) is calculated by determining the ratio of oxygen uptake to power output during the last 30s of each stage.

20 minute cycling performance test

After 15 minutes of seated rest, participants complete a 20 minute cycling performance test where they are instructed to exert maximal effort throughout the 20 minute period. RPE and HR are monitored at 5 minute intervals throughout the test. Mean power output and total work are calculated and used as performance markers for this test.

Dietary controls

A 7 day weighed food diary is administered before the beginning of the HIIT intervention in order to characterise habitual dietary intake and analyse each participant's energy and macronutrient intake. Participants are instructed to maintain their habitual dietary intake throughout the HIIT intervention. A 24 h dietary recall is conducted upon each visit to the lab for participants, and dietary analysis using this information is compared with the 7 day food diary analysis to assess maintenance of habitual dietary intake for the duration of the HIIT intervention.

Nutritional intervention

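### The protocol and SAP name no primary outcome, and testing every outcome at 0.05 leaves error across outcomes uncontrolled

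*Combined protocol and SAP*

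**What the plan says.** The Statistical Analysis Plan is one paragraph and gives four rules:

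- Within groups: "Paired sample t-tests will be used to assess within group changes".
- Between groups: "Between group treatment effects will be evaluated using a One-way ANOVA to examine the main effects of treatment based on delta scores", the delta running from before to after the intervention.
- After a significant ANOVA: "If the ANOVA yields a significant effect, post hoc comparisons will be performed using a bonferroni correction".
- Threshold: "A probability level P < 0.05 will be considered statistically significant".

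It does not say which outcomes these rules apply to, and no section designates a primary outcome or ranks outcomes.

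Several outcomes are measured before and after. On the battery, Pre-intervention performance testing says: "This comprises in order a baseline i) Wingate test; ii) Submaximal incremental cycling test; iii) 20 minute cycling performance test". Under Post-intervention performance testing, that battery "is repeated by participants in an identical manner 72-96 h following completion of the final HIIT session". The submaximal test yields "Power output at the lactate threshold" and an economy measure: "Cycling economy (CE) is calculated by determining the ratio of oxygen uptake to power output during the last 30s of each stage". The 20-minute test yields mean power and total work. No markers are named for the Wingate test in this battery. Peak power, mean power, total work and fatigue index are named only for the HIIT sessions and sprints, under Experimental design. Muscle and blood samples are also taken before and after, with no analytes named.

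**The concern.** If several outcomes are each tested at 0.05 and none is singled out, the chance that something is significant grows with the number tested. A reader of the results cannot tell from this document whether a reported difference was the planned answer or the most favourable of several. The Bonferroni step does not help with this. It follows one significant ANOVA, so it naturally refers to the three comparisons among placebo, WPC and WPH for that outcome.

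The within-group paired t-tests raise a related problem. They do not compare groups, yet a significant change in a whey arm beside a non-significant change in placebo is easily read as a benefit of whey, even when all arms changed equally.

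**Working it through.** The documents give no sample size, SD, effect size or error target across outcomes, so there is no design figure to reproduce. The check applies the SAP's rules as written and asks how often they produce a false result.

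**Inputs from the documents.** Three arms; one-way ANOVA on delta scores at 0.05; Bonferroni on three pairs, so 0.05/3 = 0.0167 per pair.

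**Count of outcomes.** The repeated battery gives four distinct markers: lactate-threshold power, cycling economy, 20-minute mean power and one Wingate marker. Total work in the 20-minute test is not counted, because it equals mean power × 1200 s for anyone who completes it. The baseline VO₂max test is not counted, because it belongs to screening and not to the repeated battery. If the Wingate contributes peak power, mean power and fatigue index (an assumption, borrowing the HIIT-session names), the count is 3 + 3 = 6. Muscle and blood analytes would add to either count.

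**Assumptions.** No true group difference; 10 per arm; two-sided tests; equal correlation r between markers, from 0 to 0.7.

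**Step 1: independent outcomes.** The chance of at least one significant ANOVA among k is 1 − 0.95^k.

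- k = 4: 1 − 0.95⁴ = 0.185
- k = 6: 1 − 0.95⁶ = 0.265

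**Step 2: correlated outcomes, by simulation.** For each marker F = MSB/MSW on 2 and 27 df. If p < 0.05, each pair is tested with t = (difference in means)/√(2·MSW/10) and its p-value is multiplied by 3.

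| Event under no true difference | 1 marker | 4 markers | 6 markers |
|---|---|---|---|
| Any significant ANOVA, r = 0 / 0.5 / 0.7 | 0.049 / 0.051 / 0.051 | 0.187 / 0.162 / 0.135 | 0.266 / 0.217 / 0.175 |
| Any Bonferroni-significant pair, any direction | about 4% | 12-16% | 15-23% |
| Whey over placebo after Bonferroni, r = 0 / 0.5 / 0.7 | 0.015 / 0.016 / 0.015 | 0.060 / 0.052 / 0.043 | 0.089 / 0.069 / 0.057 |

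For four markers the whey-over-placebo rate is 0.043/0.015 = 2.9 to 0.060/0.015 = 4.0 times the one-marker rate.

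**Step 3: sensitivity.** The any-ANOVA rate for four markers (r = 0 / 0.7) is 0.185 / 0.138 at 8 per arm and 0.185 / 0.134 at 15 per arm. At r = 0.8 with 10 per arm, four markers still give 11.9% for any ANOVA and 10.2% for any Bonferroni-significant pair.

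**Step 4: paired t-tests, one outcome, equal true change in all arms.** Let p be the chance that one arm shows a significant improvement. The chance that at least one whey arm does and placebo does not is [1 − (1 − p)²](1 − p). Its maximum is at 1 − p = 1/√3, where it equals 2/(3√3) = 0.385. With 10 per arm and a true change of 0.3 / 0.5 / 0.7 / 0.8 / 1.0 SD of the change score, simulation gives 0.217 / 0.353 / 0.375 / 0.328 / 0.188. With no change, p = 0.025 and the result is (1 − 0.975²) × 0.975 = 0.048. At 1.5 SD it is about 1%.

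**The case against.** **The harmful error is smaller than the headline.** A significant ANOVA includes whey worse than placebo and WPC differing from WPH, and the SAP requires a Bonferroni step before any pair is declared different. This stands. A reader might infer that any marker with p < 0.05 can be reported as a whey benefit, but the SAP does not permit that. The directional figure is 4-6% for four markers. It exceeds 5% only in part of the range, though it is three to four times the one-marker rate. Counting false pairs in any direction, 12-16% remains.

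**Larger counts are tempting but unsupported.** Counting session-level markers would give seven outcomes. The ANOVA, however, is on pre-to-post deltas, the SAP does not say that a change from session 1 to session 9 is such a delta, and the number of sprints rises from 4 to 6 over the sessions. Counting economy at each of five stages would give eight. Stages of one test may correlate above 0.7 (at r = 0.8, eight outcomes give 16.6% for any ANOVA), and participants may stop before 250 W.

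**A primary outcome may be designated elsewhere.** The document carries a registry number, and that record was not available here. A reader might infer that no outcome was designated in advance anywhere. The supportable statement is that this protocol and SAP designate none.

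**The study may be exploratory.** If so, labelling could suffice. But the SAP does not say so; it sets a significance threshold for treatment effects.

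**The paired tests are assigned to within-group change, not to treatment effects.** That is correct, and nothing says a whey-only result will be read as a benefit. The 19-38% also depends on an assumed change of 0.3-1.0 SD; outside that window it falls, to about 9% at 0.1 SD and 8% at 1.2 SD.

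**Conclusion.** The point holds for this document. It names no primary outcome, applies 0.05 to each outcome, and corrects only for group pairs within an outcome. That last part is the natural reading of the Bonferroni sentence; the SAP does not define the family.

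The best-grounded size is for four markers: about 4-6% for a false whey-over-placebo claim, 12-16% for any false pair and 13-19% for any significant ANOVA, against about 1.5%, 4% and 5% for a single marker. With six markers, which assumes three from the Wingate, the figures are about 6-9%, 15-23% and 17-27%. All rest on 10 per arm and correlation 0 to 0.7; group size between 8 and 15 hardly matters, and stronger correlation lowers them. The any-ANOVA rate exceeds 5% in every multi-marker case tried.

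The paired-test figure (19-38% for one outcome) is conditional on a moderate equal change in all arms. It is a reason to label those tests clearly. It does not show that the SAP will misuse them.

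**What to change.** Before outcome data are analysed by group:

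1. Designate one primary outcome and test its ANOVA at 0.05, with Bonferroni on the group pairs. The choice is the sponsor's; 20-minute mean power is one example.
2. List the distinct secondary outcomes, stating which Wingate markers and which economy stages are included. Test their ANOVAs with Holm, or label them exploratory. Use only one of 20-minute mean power and total work.
3. Decide whether overall error is to be 5%. With the primary at 0.05 and Holm over three secondaries, the chance of any false ANOVA is still 7.6-9.8% (r = 0.7 to 0). Testing the secondaries only when the primary is significant removes this excess when no outcome truly differs.
4. If 5% is to cover pairwise claims as well, gating the ANOVAs is not enough. With WPC truly 2 SD better on every outcome, WPH equal to placebo and pairs left at 0.05/3, a false WPH-placebo difference appears in 5-6% of trials for four outcomes and 7-9% for six. The procedure must then also cover the pairs across outcomes. For example, a single Holm procedure over 3 × 4 = 12 pairs starts at 0.05/12 = 0.0042.
5. Use a false-discovery-rate method only if the SAP states that it does not control familywise error.
6. Label the within-group paired t-tests descriptive, not evidence of a treatment effect.

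If group-level analysis has already begun, which the document's 2018 date makes possible, report all between-group results as exploratory instead.

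The cost is a short SAP edit and one decision by the sponsor; no new data are needed. Some secondary results will lose nominal significance, and step 4 also makes the primary pairs harder to declare if they are included in the common procedure.
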